9.1.2.1. Static Physician's Global Assessment

Both sPGA (0) and sPGA (0,1) will be assessed at various time points up to 4 years. For assessment description, see Section 9.1.1.1.

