- added a summary for treatment disposition
- added patient characteristic reporting for Visit 1 of Study AMAH in addition to the baseline of originating studies for measures that may change over time
- included definition and summary for prior medications
- updated Table AMAH.5.3 and Table AMAH.5.4 with additional details, including:
 - clarification of definitions of missing components
 - addition of sPGA(0)
 - addition of PASI 75
 - addition of PSS signs score
 - addition of PSSI score = 0
 - addition of NAPSI score = 0
 - addition of PPASI 50, PPASI 75, and PPASI 100
 - addition of DLQI (0,1) and DLQI total score ≥ 5 improvement from baseline
- added summaries to characterize patients that increase dosing
- added the analysis section for Japan submission and the Appendix of Analysis Plan for the Japan Addendum
- updated guidelines on interim database locks
- made other minor typographical corrections and clarifications not affecting content

4. Study Objectives

Table AMAH.4.1 shows the protocol defined objectives and endpoints of the study. The estimand (ICH E9 R1) associated with each endpoint/analysis is documented in the following places:

- The population and cohort of interest is described in the protocol inclusion/exclusion criteria and in this document in Section 6.1.1.
- The endpoints/variables are listed in Table AMAH.4.1, Table AMAH.6.3 and Table AMAH.6.4.
- The handling of intercurrent events is summarized in Sections 6.3.
- Population level summary measures are described in Section 6.9 and Table AMAH.6.4.

Table AMAH.4.1. Protocol Defined Objectives and Endpoints

Objectives	Endpoints

Primary
 
To evaluate the long-term maintenance of efficacy of mirikizumab in patients with moderate-to-severe plaque psoriasis
	
Over the duration of the study:
 
 • Proportion of patients with an sPGA (0,1) among those who entered Study AMAH with sPGA (0,1) • Proportion of patients who maintained a $\geq 90\%$ improvement in PASI (PASI 90) among those who entered Study AMAH with a PASI 90 response

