6.1.3. Analysis Methods

For assessments of the primary endpoints and other binary efficacy and health outcomes, proportions for each cohort along with the 95% 2-sided asymptotic (i.e., not continuity corrected) confidence intervals (CIs) will be provided. Modified Non-responder Imputation (mNRI) method will be used to estimate the percentage of patients achieving response across post-baseline visits (see Section 6.3.4). In addition, multiple imputation (MI), Non-responder Imputation (NRI), and as Observed methods will be used as secondary analysis (see Section 6.3.1, Section 6.3.2, Section 6.3.1).

For continuous efficacy and health outcomes, MI method will be used for summaries.

Summaries based on observed data at each post-baseline visit will be provided (see Section 6.3.1).

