		PPASI 75	A \geq 75% improvement in PPASI score from baseline	Missing if baseline or observed value is missing.

Measure	Description	Variable	Derivation/Comment	Definition of Missing/duplicate Components
		PPASI 100	a 100% improvement in PPASI score from baseline	Missing if baseline or observed value is missing.
DLQI	Dermatology Life Quality Index (DLQI): is a validated, dermatology-specific, patient-reported measure that evaluates patient’s health-related QoL. This questionnaire has 10 items that are grouped in 6 domains, including symptoms and feelings, daily activities, leisure, work and school, personal relationships, and treatment. The recall period of this scale is over the “last week.” Response categories and corresponding scores are: Very much = 3 A lot = 2 A little = 1 Not at all = 0 Not relevant = 0	DLQI total score	A DLQI total score is calculated by summing all 10 question responses, and has a range of 0 to 30 (less to more impairment) (Finlay and Khan 1994; Basra et al. 2008).	If 2 or more questions are missing, the total score is missing. Note: #7B could be a valid missing while #7A is not “No.” That is, #7 should be considered as 1 question.
		DLQI (0,1)	A DLQI (0,1) response is defined as a post-baseline DLQI total score of 0 or 1. A DLQI total score of 0 to 1 is considered as having no effect on a patient’s HRQoL (Khilji et al. 2002; Hongbo et al. 2005).	Missing if DLQI total score is missing.
		DLQI (0,1) and DLQI total score ≥ 5 improvement from baseline	Patient is a DLQI (0,1) responder and reduction/decrease of ≥ 5 points from baseline	Missing if baseline or the total score is missing.

Abbreviations: DLQI = Global Assessment Dermatology Life Quality Index; HRQoL = health-related quality of life; NRS = Numeric Rating Scales; SAP = statistical analysis plan; PASI = Psoriasis Area and Severity Index; PSS = Psoriasis Symptoms Scale; PSSI = Psoriasis Scalp Severity Index; sPGA = Static Physician Global Assessment.

Table AMAH.6.4. Description of Efficacy/Health Outcomes Analyses

Measure	Variable	Analysis Method (Section 6.1.3)	Population (Section 6.1.1)	Time Point
PASI	PASI 90 (Primary)	Descriptive analysis with Observed, NRI, mNRI and Multiple Imputation	ITT - patients who entered Study AMAH with a PASI 90 response	All visits in corresponding Periods
	PASI 75; PASI 90; PASI 100 (Secondary)	Descriptive analysis with Observed, NRI, mNRI and Multiple Imputation	ITT	All visits in corresponding periods

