sPGA	sPGA (0,1) (Primary)	Descriptive analysis with Observed, NRI, mNRI and Multiple Imputation	ITT - patients who entered Study AMAH with sPGA (0,1)	All visits in corresponding periods
	sPGA (0); sPGA (0,1) (Secondary)	Descriptive analysis with Observed, NRI, mNRI and Multiple Imputation	ITT	All visits in corresponding periods
PSS	PSS symptoms score of 0;	Descriptive analysis with Observed, NRI, mNRI and Multiple Imputation	ITT – patients with a PSS symptoms score ≥ 1 at Baseline	All visits in corresponding periods
	PSS signs score of 0;	Descriptive analysis with Observed, NRI, mNRI and Multiple Imputation	ITT – patients with a PSS signs score ≥ 1 at Baseline	All visits in corresponding periods
PSSI	PSSI change from baseline	Descriptive analysis with Observed and Multiple Imputation	ITT - patients with Scalp Involvement at Baseline	All visits in corresponding periods
	PSSI = 0	Descriptive analysis with Observed, NRI, mNRI and Multiple Imputation	ITT – patients with Scalp Involvement at Baseline	All visits in corresponding periods
PPASI	PPASI change from baseline	Descriptive analysis with Observed and Multiple Imputation	ITT - patients with Palmoplantar Involvement at Baseline	All visits in corresponding periods

Measure	Variable	Analysis Method (Section 6.1.3)	Population (Section 6.1.1)	Time Point
	PPASI 50; PPASI 75; PPASI 100	Descriptive analysis with Observed, NRI, mNRI and Multiple Imputation	ITT – patients with Palmoplantar Involvement at Baseline	All visits in corresponding periods
NAPSI	NAPSI change from baseline	Descriptive analysis with Observed and Multiple Imputation	ITT - patients with Nail Psoriasis Involvement at Baseline	All visits in corresponding periods
	NAPSI = 0	Descriptive analysis with Observed, NRI, mNRI and Multiple Imputation	ITT – patients with Nail Psoriasis Involvement at Baseline	All visits in corresponding periods
DLQI	DLQI (0,1)	Descriptive analysis with Observed, NRI, mNRI and Multiple Imputation	ITT - patients with Baseline DLQI > 1	All visits in corresponding periods
	DLQI (0,1) and ≥5-point reduction from Baseline	Descriptive analysis with Observed, NRI, mNRI and Multiple Imputation	ITT – patients with DLQI ≥5 at Baseline	All visits in corresponding periods

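### Maintenance of response is estimated only as visit-by-visit prevalence, with no headline visit, so continuous maintenance may be overstated by an unknown amount

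*SAP*

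**What the plan says.** SAP Table AMAH.4.1 states one primary objective, long-term maintenance of efficacy, with two endpoints framed as "Over the duration of the study". The two are worded differently:

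- PASI 90: it opens "Proportion of patients who maintained a" and goes on to an improvement of at least 90%, "among those who entered Study AMAH with a PASI 90 response".
- sPGA ("Proportion of patients with an sPGA (0,1) among those who entered Study AMAH with sPGA (0,1"): the verb *maintained* does not appear.

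Protocol 9.1.1 introduces both measures as showing how many patients keep the efficacy they reached in the originator studies. The maintenance aim therefore covers both.

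The analysis is the same for each. SAP 6.1.3 says mNRI "will be used to estimate the percentage of patients achieving response across post-baseline visits". Table AMAH.6.4 gives the time point as "All visits in corresponding Periods" for PASI 90 and "All visits in corresponding periods" for sPGA (0,1). Table AMAH.6.3 derives both responses from the score at one visit against originator baseline, with no condition on earlier visits. SAP 6.3.3 and 6.3.4 refer to a predefined time for judging response, but neither document names one.

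On dose increases, SAP 5.1 and Protocol 7.4 allow patients on 125 mg to move to 250 mg after unblinding if efficacy is lost. SAP 6.1.1 analyses patients by assigned treatment. SAP 6.9.2 plans only the number of such patients by visit and their scores before the increase. SAP 6.9.5 lists no sensitivity analyses.

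**The concern.** Prevalence at successive visits can stay flat while individual patients move in and out of response. Under mNRI, loss of response on treatment is not carried forward; only data missing after discontinuation for an adverse event (including death) or lack of efficacy are set to non-response. A patient in relapse lowers the curve at that visit and raises it again on recovery, and no planned analysis records that the response was ever lost. The primary analyses of PASI 90 and sPGA (0,1) use the same variables, methods and visits as the secondary ones. They differ only in being restricted to patients in response at entry, so the word *maintained* adds nothing to the calculation.

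In the 125 mg cohort this bears on interpretation of the dose. A patient who loses response on 125 mg and regains it on 250 mg can count as a responder in the 125 mg column.

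Because no visit is named as the headline, the figure quoted as the maintenance rate is left open. SAP 6.15 allows yearly or ad hoc interim analyses, so the quoted visit could also change with each data cut.

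**Working it through.** **The plan's own figure.** The only design number is enrolment: (205 + 1440 + 500 + 300) = 2445; 2445 × 0.8 × 0.8 = 1565 and 2445 × 0.9 × 0.9 = 1980. This agrees with the stated 1600 to 2000. No response, loss or regain rate is given for the primary endpoints, so the rates below are assumptions.

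**Inputs from the documents.** The Schedule of Activities has 20 post-entry treatment visits (Visits 2 to 21): 13 at 8-week spacing to Week 104, six at 16-week spacing to Week 200, and one 8 weeks later at Week 208.

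**Assumed model.** Every patient is in response at Week 0, data are complete, and the probabilities of loss (l) and regain (r) are constant per 8 weeks.

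- Prevalence after k steps of 8 weeks: P(k) = r/(l+r) + [l/(l+r)](1−l−r)^k, with k = 26 at Week 208.
- In response at every scheduled visit: S = (1−l)^14 × [(1−l)² + l·r]^6. The bracket covers the 16-week intervals, in which a loss and regain between visits goes unseen.

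**Example, l = 0.02 and r = 0.25.** P(26) = 0.25/0.27 + (0.02/0.27)(0.73)^26 = 92.6%. S = 0.98^14 × 0.9654^6 = 0.7536 × 0.8096 = 61.0%. The gap is 31.6 points.

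| Loss per 8 wk | Regain per 8 wk | Prevalence, Week 208 | In response at every visit | Gap (points, unrounded inputs) |
|---|---|---|---|---|
| 0.5% | 0% | 87.8% | 87.8% | 0 |
| 0.5% | 25% | 98.0% | 88.4% | 9.6 |
| 1% | 25% | 96.2% | 78.2% | 18.0 |
| 2% | 0% | 59.1% | 59.1% | 0 |
| 2% | 10% | 83.9% | 59.9% | 24.1 |
| 2% | 25% | 92.6% | 61.0% | 31.6 |
| 3% | 25% | 89.3% | 47.5% | 41.8 |
| 3% | 50% | 94.3% | 49.8% | 44.5 |

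Under one missing-data rule, prevalence cannot fall below sustained response, so the direction is fixed. The size depends on regain and is zero without it. The gap also grows with time: at Week 48, with regain 25% and loss 0.5–3%, it is 1.3 to 7.5 points.

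**Choice of headline visit.** With 2% loss, prevalence at Weeks 48 / 104 / 208 is 93.7 / 92.7 / 92.6% (regain 25%), 91.1 / 86.5 / 83.9% (regain 10%) and 88.6 / 76.9 / 59.1% (no regain). In these scenarios the two issues trade off: where regain is rare the gap closes, but the choice of visit matters most (88.6 − 59.1 = 29.5 points).

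**Dose increase in the 125 mg cohort.** The addition to prevalence is the share with an increase times the share of those who regain response. For assumed shares of 5–20% and 30–70%, it is 0.05 × 0.30 = 1.5 points to 0.20 × 0.70 = 14 points.

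**The case against.** The strongest reply is that visit prevalence is a legitimate estimand. It is unbiased by regain as an estimate of the proportion in response at a visit, it falls when patients relapse, and it is what the sPGA endpoint says. All of that stands. A reader might infer that the analysis fails to estimate the primary endpoints, or that maintenance *is* overstated. The documents do not support either as a flat statement: both require *maintained* to mean unbroken response, which is never defined, and only the PASI 90 endpoint uses the word.

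A reader might also multiply 2 endpoints × 20 visits × 4 methods × 3 cohorts to get 480 candidate headlines. That is too many. SAP 6.3.4 makes mNRI the primary method for categorical outcomes, and SAP 6.1.1 analyses the cohorts separately by design. The open choice is 20 visits per endpoint and cohort. (Protocol 10.3.1.1 names ordinary NRI as primary, which is a separate matter.)

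Selective reporting is limited by the commitment to tabulate every visit in a descriptive study without hypothesis tests. This weakens the worry, but does not settle which number is quoted as the maintenance rate.

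Protocol 9.1.2.1 says sPGA "will be assessed at various time points up to 4 years", but that section covers secondary assessments and is no evidence about the primary endpoints.

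On dose increases, the NRI text in SAP 6.3.3 asks that responders stay on assigned treatment, which might exclude these patients. Its operative rule does not mention a dose increase, and mNRI has no such condition.

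Two further points stand. A strict every-visit rule punishes noise: independent 95% response per visit gives 0.95^20 = 35.8% over 20 visits. And SAP 6.1 mentions a supplemental SAP, not available here, which might contain a sustained-response analysis.

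**Conclusion.** The point holds in a limited form. The plan sets out to show long-term maintenance, but in the documents available it estimates only response at each visit, without defining *maintained*, naming a headline visit or measuring loss. Patients who lose and regain response, including those on 125 mg who regain it after a dose increase, count as responders again. Visit prevalence may therefore overstate continuous maintenance, while remaining a valid estimate of response at a visit.

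The direction relative to continuous maintenance is certain under a common missing-data rule. The size is unknown: 0 to about 45 points at Week 208 under assumed loss of 0.5–3% and regain of 0–50% per 8 weeks, constant rates and complete data. Nothing in the documents shows which part of that range applies. The missing headline visit creates ambiguity and room for selection; it does not by itself cause overstatement.

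**What to change.** Keep the visit-wise tables and make these additions to the SAP:

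1. State what *maintained* means for PASI 90.
2. Name one headline visit with mNRI for both primary endpoints. Week 208 is one option. Since SAP Section 5 lets treatment run for about 4 years or until commercial availability, add a rule for the case that the study ends earlier.
3. For each primary endpoint and cohort, add a supportive time-to-first-loss estimate (Kaplan–Meier, loss dated to the visit where it is first seen) or a sustained-response proportion. Count discontinuation for an adverse event or lack of efficacy as loss, censor administrative ends, and say how other discontinuations are handled.
4. Do not count response regained after a dose increase as maintenance on 125 mg. The increase rests on investigator opinion, so also state how a patient still meeting the response criterion at the time of the increase is classified.

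The cost is a few sentences and one figure or table per endpoint, from assessments already scheduled; conduct does not change. The downside is that loss is interval-censored by the 8- and 16-week visits, and a single transient visit counts as loss. The new estimate should therefore be reported beside prevalence, not in its place.

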6.9.1. Primary Outcome and Methodology

Primary outcomes, sPGA (0,1) and PASI 90 and their analyses are described in [Table AMAH.6.3](#) and [Table AMAH.6.4](#).

6.9.2. Additional Analyses of the Primary Outcome

Additional analyses of the primary outcomes are described in [Table AMAH.6.3](#) and [Table AMAH.6.4](#).

After Study AMAH dosing is no longer blinded, patients may be increased from 125 mg mirikizumab Q8W to 250 mg mirikizumab Q8W. Additional summaries to characterize the patients that increase dosing will be presented. These summaries include:

- The number of patients who increase dosing of mirikizumab by visit
- sPGA and PASI scores or other measurements at the visit prior to titration of mirikizumab

6.9.3. Multiple Testing Controlled Secondary Efficacy Analyses

Not Applicable.

6.9.4. Secondary Efficacy Analyses

Other secondary analyses of efficacy are described in [Table AMAH.6.3](#) and [Table AMAH.6.4](#).

6.9.5. Sensitivity Analyses

Not Applicable.

6.10. Health Outcomes/Quality-of-Life Analyses

Secondary analysis of health outcomes/quality of life are described in [Table AMAH.6.3](#).

6.11. Bioanalytical and Pharmacokinetic/Pharmacodynamic Methods

Details of pharmacokinetic/pharmacodynamic (PK/PD) analyses can be found in a separate PK/PD analysis plan.

6.12. Safety Analyses

For the purpose of Study AMAH alone, the following are planned:

- Listing of Serious Adverse Events (SAEs)
- Listing of adverse events leading to permanent discontinuation of study drug
- Summary of SAEs (with different columns for cohorts specified in Section [6.1.1](#))
- Summary of AEs leading to permanent discontinuation of study drug (with different columns for cohorts specified in Section [6.1.1](#))

The safety data from this study will also be used as part of integrated safety assessments and ongoing safety review through study end.

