10.3. Statistical Analyses

10.3.1. General Statistical Considerations

Statistical analysis of this study will be the responsibility of Lilly or its designee.

Any change to the data analysis methods described in the protocol will require an amendment ONLY if it changes a principal feature of the protocol. Any other change to the data analysis methods described in the protocol, and the justification for making the change, will be described in the clinical study report. Additional exploratory analyses of the data will be conducted as deemed appropriate.

For all safety, efficacy and health outcomes analysis, the ITT population will be used unless otherwise stated.

Continuous data will be summarized in terms of the mean, standard deviation, minimum, maximum, median, and number of observations. Categorical data will be summarized as frequency counts and percentages. The analysis will be focused on point estimates and confidence intervals. Thus, no hypothesis testing will be performed, and control for multiplicity is not applicable. Efficacy and safety summaries will be provided by the following 3 cohorts:

- (1) Patients assigned to 250 mg mirikizumab Q8W SC in Study AMAH, excluding patients who received secukinumab during the qualifying period of their originating study.
- (2) Patients assigned to 125 mg mirikizumab Q8W SC in Study AMAH
- (3) Patients who received secukinumab during the qualifying period of their originating study.

Additional cohorts for further analysis may be defined in the SAP and summarized. Sensitivity analyses may be done by excluding from Cohort (1) patients who were receiving placebo during the qualifying period of their originator study.

Unless otherwise specified, all references to baseline for efficacy and health outcomes related endpoints in this study protocol refer to baseline values of the originating study. Detailed definitions of baseline for safety, vital sign, laboratory, and immunogenicity related analyses will be described in the SAP prior to first unblinded analysis.

For assessment of categorical efficacy endpoints, proportions and 95% confidence intervals will be reported using the simple asymptotic method, without continuity correction (that is, normal approximation to the binomial distribution).

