10.3.4. Safety Analyses

Safety assessments will include AEs, laboratory analytes, vital signs, ECGs, and C-SSRS. Safety data assessments will be summarized for the cohorts described in Section [10.3.1](#)

Adverse events will be coded according to the *Medical Dictionary for Regulatory Activities* and summarized by system organ class, preferred term, severity, and relationship to investigational product. A treatment-emergent adverse event (TEAE) is defined as an event that first occurred or worsened in severity after baseline. For each event classification term, the number of patients experiencing a TEAE with that classification term will be tabulated.

Treatment-related TEAEs are defined as events that are indicated by the investigator on the eCRF to be related to study treatment. If a patient reports the occurrence of a particular event more than once, the most severe of those events will be included in the summary table of TEAEs. For events that are gender specific, the denominator and computation of the percentage will only include patients from the given gender.

Adverse events of special interest are defined in Section [9.2.3](#), and the plan for analyzing AESIs will be described in the Program Safety Analysis Plan and SAP.

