6.12.1. Extent of Exposure

The exposure will be calculated as:

Date of last study visit during the treatment period – Date of first dose for the treatment period of Study AMAH+1 day

Overall exposure will be summarized in total patient years (PY), derived in the following manner:

$$\text{Exposure in PY} = \text{Sum of duration of exposure in days (for all patients in treatment group)} / 365.25.$$

Total PY of exposure will be reported. Descriptive statistics will be provided for patient-weeks of exposure and the frequency of patients falling into different exposure ranges will be summarized:

- >0; ≥ 24 weeks; ≥ 48 weeks; ≥ 72 weeks; ≥ 96 weeks; ≥ 120 weeks; ≥ 152 weeks; ≥ 184 weeks; ≥ 208 weeks
- >0 to <24 weeks; ≥ 24 weeks to <48 weeks; ≥ 48 weeks to <72 weeks; ≥ 72 weeks to <96; ≥ 96 weeks to <120; ≥ 120 weeks to <152; ≥ 152 weeks to <184 weeks; ≥ 184 weeks to <208 weeks; ≥ 208 weeks.

Additional exposure ranges may be considered, if necessary. No p-values will be reported in these tables as they are intended to describe the study populations, rather than test hypotheses about them.

A by-patient listing of assigned treatments will be provided.

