6.15. Interim Analyses and Data Monitoring

Data Monitoring Committee (DMC): One DMC, consisting of members external to Lilly, will be established for interim safety monitoring across Studies I6T-MC-AMAK, I6T-MC-AMAJ, I6T-MC-AMAH and I6T-MC-AMBK in patients with psoriasis. This committee will consist of a minimum of 3 members, including a physician with expertise in dermatology and a statistician. No member of the DMC may have contact with study sites. A Statistical Analysis Center (SAC) will prepare and provide unblinded safety data to the DMC. The SAC members may be Lilly employees or from third-party organizations designated by Lilly. However, they will be external to the study team and will have no contact with sites and no privileges to influence any change in the ongoing study. Access to the unblinded safety data will be limited to the DMC and the SAC or their designees. The study team will not have access to the unblinded data. Only the DMC is authorized to evaluate unblinded data. The purpose of the DMC is to advise Lilly regarding continuing patient safety; however, the DMC may request key efficacy data to put safety observations into context and to confirm a reasonable benefit/risk profile for ongoing patients in the study. Study sites will receive information about interim assessments ONLY if they need to know for the safety of their patients. This committee will make recommendations as to whether it is scientifically and ethically appropriate to continue enrollment, discontinue a treatment group, or discontinue the study. Details outlining the roles and responsibilities of the DMC will be finalized in the DMC charter.

Interim Database Lock: An unblinded interim analysis may be performed to support a regulatory submission. Additional yearly or ad-hoc interim analysis may be performed along with the 4-month safety update or to meet any external regulatory needs.

Final Database Lock: A final database lock will occur after the Post-Treatment Follow-Up Period is completed.

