6.17. Clinical Trial Registry Analyses

Additional analyses will be performed for the purpose of fulfilling the Clinical Trial Registry (CTR) requirements.

Analyses provided for the CTR requirements include the following:

Summary of AEs, provided as a dataset which will be converted to an XML file. Both SAEs and “Other” AEs are summarized by treatment group, by MedDRA preferred term.

- An AE is considered “Serious,” whether or not it is a TEAE.
- An AE is considered in the “Other” category if it is both a TEAE and is not serious. For each SAE and “Other” AE, for each term and treatment group, the following are provided:
 - the number of participants at risk of an event
 - the number of participants who experienced each event term
 - the number of events experienced.
- Consistent with www.ClinicalTrials.gov requirements, “Other” AEs that occur in fewer than 5% of patients/subjects in every treatment group may not be included if a 5% threshold is chosen (5% is the minimum threshold).
- AE reporting is consistent with other document disclosures for example, the CSR, manuscripts, and so forth.

7. Unblinding Plan

Refer to a separate blinding and unblinding plan.

8. References

- Heitjan F. and Little RJA. (1991), Multiple imputation for the fatal accident reporting system. *Applied Statistics*. 1991;40:13–29.
- PhUSE resouces page. Analyses and Displays Associated with Outliers or Shifts from Normal to Abnormal: Focus on Vital Signs, Electrocardiogram, and Laboratory Analyte Measurements in Phase 2-4 Clinical Trials and Integrated Summary Documents. 2015. Available at http://www.phusewiki.org/docs/CSS%20White%20Papers%202016/CS_WhitePaper_Outliers_Shifts_v1.0.pdf. Accessed September 18, 2017.
- Schenker N. and Taylor JMG. (1996), Partially parametric techniques for multiple imputation. *Computational Statistics and Data Analysis*. 1996;22:425–446.

9. Appendices

[figure not shown]

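### SAP 6.12 specifies no exposure adjustment for the SAE and discontinuation-AE summaries by cohort, so the default percentages depend on length of follow-up

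*SAP*

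**What the plan says.** SAP 6.12 limits its list to Study AMAH alone. It contains two listings (SAEs, and AEs leading to permanent discontinuation of study drug) and two summaries of the same events: "Summary of SAEs (with different columns for cohorts specified in Section" 6.1.1) and "Summary of AEs leading to permanent discontinuation of study drug (with different columns for cohorts specified in Section" 6.1.1). No metric, time at risk or censoring rule is given. The section adds that the data will also feed integrated safety assessments.

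Where a metric is stated elsewhere, it counts persons:
- Protocol 10.3.1: "Categorical data will be summarized as frequency counts and percentages".
- Protocol 10.3.4: "the number of patients experiencing a TEAE with that classification term will be tabulated".
- SAP 6.17, for the registry tables: "the number of participants at risk of an event".

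SAP 6.12.1 defines exposure per patient, from first dose to the last treatment-period visit, and then: "Overall exposure will be summarized in total patient years (PY), derived in the following manner". Its stated use is "Total PY of exposure will be reported", with patient-weeks and exposure bands from above 0 to at least 208 weeks. On data cuts, SAP 6.15 says: "Additional yearly or ad-hoc interim analysis may be performed along with the 4-month safety update".

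**The concern.** The study's title puts long-term safety first, and these two summaries are the main safety tables that the SAP commits to for AMAH itself. They set three cohorts side by side, which invites comparison.

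The percentage of patients with at least one event rises with time observed. If one cohort is followed for less time on average, its percentage is lower at the same underlying rate. If the table is repeated at a later cut, the percentage rises although the rate has not changed. A reader could see a difference between dose cohorts that is only a difference in follow-up, or miss a real one.

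Follow-up can differ in three ways:
- **Dropout** before week 208, at any analysis.
- **Interim cuts** (SAP 6.15, Protocol 10.3.8), when patients who entered at different dates have unequal exposure.
- **An early stop.** Protocol 5.1 and SAP 5 let treatment run about 4 years or until commercial availability, and a calendar stop would truncate late entrants.

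**Working it through.** **The plan's own figures.** Neither document gives an SAE rate, a dropout rate or an expected patient-year total, so there is no plan figure on this point to reproduce. Enrolment does reproduce: 205 + 1440 + 500 + 300 = 2445; 2445 × 0.80 × 0.80 = 1565 and 2445 × 0.90 × 0.90 = 1980, against the stated 1600 to 2000. It does not bear on this question.

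**Input from the documents.** Maximum treatment is 208 weeks: T = 208 × 7 / 365.25 = 3.99 years.

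**Assumed inputs.** A constant first-SAE rate L, the same in every cohort (3, 5 or 10 per 100 patient-years), and a constant dropout rate d, independent of SAE risk (0.05 to 0.30 per year).

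**Formulas, per patient.**
- Proportion with an SAE by T: L/(L+d) × (1 − exp(−(L+d)T))
- Years at risk to first SAE, dropout or T: (1 − exp(−(L+d)T))/(L+d)
- Rate: the first divided by the second, which equals L

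**Worked case, L = 0.05.**
- d = 0.05: 0.5 × (1 − exp(−0.10 × 3.99)) = 16.4%; years at risk 3.29; 0.164/3.29 = 5.0 per 100.
- d = 0.30: (0.05/0.35) × (1 − exp(−0.35 × 3.99)) = 10.7%; years at risk 2.15; 0.107/2.15 = 5.0 per 100.

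**Percentage with an SAE by week 208.**

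| True rate per 100 PY | d = 0.05 | d = 0.10 | d = 0.20 | d = 0.30 |
|---|---|---|---|---|
| 3 | 10.2% | 9.3% | 7.8% | 6.7% |
| 5 | 16.4% | 15.0% | 12.6% | 10.7% |
| 10 | 30.0% | 27.5% | 23.3% | 19.9% |

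Within a row the rate per 100 patient-years is constant. At 5 per 100, the outer columns differ by 16.4 − 10.7 = 5.7 points, and d = 0.05 against 0.10 by 1.4 points. Equal dropout gives no difference. The outer pair is a wide contrast: by T, 1 − exp(−0.05 × 3.99) = 18% have left in one group and 1 − exp(−0.30 × 3.99) = 70% in the other.

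**Successive cuts, no dropout, 5 per 100.** The proportion is 1 − exp(−0.05t): 4.9% at 1 year, 9.5% at 2 years, 13.9% at 3 years and 18.1% at week 208.

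**The case against.** The strongest reply is that SAP 6.12 never says crude. It says only that there will be a summary, and a rate could be produced under that word. A reader might infer that the SAP prescribes crude counts, but it does not. The reading comes from the protocol defaults, which the SAP leaves in place for these tables.

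A reader might also infer that patient-years are never used as a denominator anywhere in the programme. That cannot be said. SAP 6.12 points to integrated assessments, and Protocol 10.3.4 refers events of special interest to a Program Safety Analysis Plan as well as the SAP. Neither method is shown.

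The causes must not be stretched either. A dose increase does not change a patient's total time at risk, and analysis is by assigned treatment (SAP 6.1.1). Planned treatment runs to week 208 for everyone, so entry date has no effect at a final lock after full follow-up. Nothing in the documents says that dropout will differ between cohorts.

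A reader could also form a rough rate from the reported patient-years. In the worked case, mean exposure is 3.61 and 2.33 years, giving 16.4/3.61 = 4.5 and 10.7/2.33 = 4.6 per 100. That removes most of the artefact, so it is too strong to say that cuts cannot be compared at all. It still falls short of 5.0, because time after the first event is counted, and it comes without an interval.

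Finally, cohorts follow prior treatment and nothing is tested. Rates would not make the contrast causal. That stands, but a descriptive figure that tracks follow-up length can still mislead.

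**Conclusion.** The point holds as a gap in specification that is cheap to close. Followed as written, the AMAH-only summaries default to patient counts and percentages, and the patient-years in SAP 6.12.1 are not connected to any event table in these two documents. No sample size, power or error rate is affected. What suffers is the reading of the cohort columns and of successive data cuts.

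The size is illustrative. At an assumed 5 first SAEs per 100 patient-years everywhere, the artefact by week 208 runs from nil with equal follow-up, through 1.4 points for a modest dropout difference, to 5.7 points for a wide one. Over the assumed rates of 3 to 10 per 100, the wide contrast gives 10.2 − 6.7 = 3.5 to 30.0 − 19.9 = 10.1 points. These figures assume constant hazards and dropout unrelated to SAE risk. The change between cuts does not depend on any cohort difference and is certain to occur if the table is repeated as follow-up accumulates.

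**What to change.** In SAP 6.12, for both summaries and by cohort, add beside n (%) the number of patients with an event per 100 patient-years at risk, with a 95% CI and the interval method named. Define time at risk as first AMAH dose to first event or end of observation, whichever is earlier.

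Use the same window for numerator and denominator, and say whether the 12-week follow-up belongs to it. This needs stating because the Schedule of Activities collects adverse events at Visits 801 and 802, while exposure in SAP 6.12.1 stops at the last treatment-period visit.

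Keep analysis by assigned cohort as the main table. Showing 125 mg time before and after a dose increase is an optional descriptive supplement: patients who increase are selected for loss of efficacy, so the two periods do not compare like with like.

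The cost is a few columns and one derivation. SAP 6.12.1 gives total exposure, not time to first event, so the latter must be derived from dates already collected. The rate also assumes a roughly constant hazard, which is a reason to keep n (%) beside it.
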